### Exclusion Criteria:

- Breastfeeding women and pregnant women, or women of child bearing potential who are not using a medically accepted means of contraception (to include oral, injectable, or implant birth control, condom, diaphragm with spermicide, intrauterine device, tubal ligation, abstinence, or partner with vasectomy);
- Current, ongoing serious suicidal risk as assessed by evaluating investigator or by scoring 5 or more on the item-10 of the MADRS.
- Unstable medical illness as determined by the investigator;
- Patients with schizophrenia or schizoaffective disorders (current or past);
- Substance use disorder during the 3 months prior to screening; except for Cannabis and Alcohol use Disorders.
- Clinical evidence of untreated hypothyroidism;
- Patients with any evidence of clinically significant liver abnormalities, or any liver transaminase level > 1.5 x ULN at initial screening, or > 5 x ULN during treatment;
- Axis II personality disorders that are the primary purpose of treatment, or would interfere with a patient's safety or compliance, as determined by the investigator during open-ended psychiatric interview;
- Patients currently being treated for a respiratory disorder (including asthma or COPD);
- For participants over the age of 60, evidence of dementia as determined by the St. Luis University Mental Status Exam (SLUMS; participants with total scores less than or equal to 20 will be excluded and referred to their Primary Care Physician for follow-up/dementia evaluation);

Structured psychotherapy focused on treatment of PTSD is exclusionary unless the subject has had at least 8 weeks of treatment prior to starting the study medication;

[figure not shown]
- **8. Privacy:** All reports generated from the data obtained through this study will protect the confidentiality of the subjects who participate in this study. All subjects will be given a "wallet card" which identifies them as a study participant and lists the emergency contact numbers. If a subject shows clinical deterioration (worsening of PTSD symptoms), [name] will determine whether: 1) the subject can remain in the study, or; 2) a higher level of care (e.g. referral back to treating psychiatrist or referral to emergency or inpatient care) is needed.

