- **9. Selection**: Subject eligibility will first be assessed via telephone screening and if records are available, by a preliminary medical record review. If the subject seems to be a likely candidate for inclusion in this protocol, he or she will be evaluated for study eligibility in person. Telephone screens will occur by experienced research personnel adept with this process. Following a face-to-face evaluation and discussion with the research team, an experienced study investigator will determine suitability for enrollment.
- 10. Recruitment: Subjects will be recruited through flyers, public advertisement (newspaper, radio, internet posting), by word of mouth, contact with community service groups, our local IRB-approved screening protocol (KW0003), and clinics and local treatment facilities (e.g., VA Hospital, Community-Based Outpatient Clinics, local private practices). Subjects will be identified via their response to advertisements and/or internal recruiting through the research clinics. Subjects will be asked to call us at the number provided on the flyers if they are interested in participating in the research study. Subjects will be contacted for follow-up appointments via the most convenient means and personal preference, e.g. telephone. All available research staff is responsible for recruiting potential subjects.
- 11. Research Plan: This study will be conducted at the VA Hospital, West Haven, CT.

Overview: This is a diagnosis-informed study designed to provide preliminary data regarding the efficacy and tolerability of riluzole to treat symptoms of PTSD. Subjects diagnosed with PTSD will receive riluzole, 50 mg taken twice daily (BID) for 12 weeks. PTSD subjects will be followed closely on a weekly basis and their liver function and pregnancy tests will be repeated (see Table 1).

Dosing: Following confirmation of eligibility, the dosing regimen for the first week of study medication is 50 mg twice a day (BID). Subjects who are unable to tolerate the study medication will be allowed to take a lower dose. For these subjects, the dose may be lowered to 50 mg taken once a day (QD). Subjects who are unable to tolerate the once a day 50 mg (QD) dosing regimen will be discontinued from the study. Riluzole should be taken 1 hour before or 2 hours after a meal to avoid food-related decreases in bioavailability.

A schedule of the study events is provided in Table 1.

Figure 1. Study Design

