- A. Participants: Twenty patients with a current diagnosis of PTSD or sub-threshold PTSD between the ages of 18-75 will complete the treatment phase of the study. Subjects will initially be pre-screened by phone interview and a preliminary medical record review. Eligible subjects will then be invited for an in-office visit and will complete the written informed consent process. Subjects will be thoroughly screened for inclusion and exclusion criteria as described below.
- B. Discontinuation of subjects: Subjects may be discontinued from study treatment and assessments at any time. Specific reasons for discontinuing a subject from this study are:
  - Voluntary discontinuation by the subject, who is at any time free to discontinue his/her participation in the study without prejudice to further treatment;
  - Clinical deterioration: The following are objective criteria for clinical deterioration, (1) a 35% increase in CAPS scores at any time during the study, (2) Patients with a CGI-I score ≥ 6 at any post-baseline visit, and (3) the onset of active suicidality as assessed by the study investigator or by scoring 5 or more on the item-10 of MADRS;
  - Evidence of neutropenia (ANC ≤ 1500) or other intolerable adverse reaction, or unable to tolerate study drug;
  - Transaminase levels > 5x ULN;
  - Safety reasons as judged by the investigator;
  - Stopping birth control or positive pregnancy test;
  - Evidence of illicit drug abuse (except for cannabis) or problematic alcohol use during trial;
  - Non-compliance to protocol as judged by the investigator; Subjects who do not take between 75-125% of study medication for two consecutive visits are considered non-adherent and are withdrawn from the study medication.

A subject that prematurely discontinues (i.e. stops study medication or no longer wishes to participate) will always be asked about the reason(s) for discontinuation and the presence of any adverse events. If possible, they will be seen and assessed by the investigator. Adverse events will be followed up as medically necessary.

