- C. Screening Procedures and Behavioral Assessments: A waiver of HIPAA authorization and written informed consent will be obtained for a brief initial phone screen and preliminary medical record review. The phone screen and preliminary medical record review will be done to determine obvious exclusions from the study protocol and to prevent subjects from making unnecessary travel for screening as well as possibily delaying the start of other treatments. Potentially eligible subjects will then be invited for an in-office screening visit, sign the VA informed consent, the VA HIPAA, be personally interviewed and begin the medical assessments. All subjects will have an initial screening assessment that includes medical history, physical examination, laboratory testing, psychiatric history and standardized psychiatric assessments.
- C.1. Historical and Demographic Information: Each subject will complete a demographic information form. This document will elicit information about the subjects' demographics including education level, socioeconomic status, race and ethnicity. In addition, it will also request information on the subject's family history of mental illness.
- C.2. Screening Physical Exam and Laboratories: All subjects will have a standard physical examination (including neurological examination) conducted by a physician/APRN at the time of the initial screening. Routine laboratory studies include CBC, CMP, baseline HCG, TSH, fT4, RPR, ESR, CRP, urinalysis, and urine toxicology screen. An ECG will also be obtained. Additional tests will be requested as clinically indicated.
- C.3. Screening and Behavioral Assessments: PTSD subjects will have an open ended psychiatric interview, in addition to a structured clinical interview (i.e. SCID or MINI). Baseline and follow-up ratings will also be obtained via assessment measures of PTSD, trauma, depression, anxiety, sleep, alcohol use, and adverse effects. Subjects will also complete a computerized neuropsychological test battery called 'Cogstate' (see Table 1).

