Riluzole: Most side effects are usually mild and resolve after stopping the drug. The most commonly observed adverse reactions of riluzole, dosed at 100mg/day, in placebocontrolled trials were asthenia (19.2%), nausea (16.3%), decreased lung functioning (10.2%), headache (7.3%), rhinitis (6.4%), hypertonia (6.1%), hypertension (5.1%), abdominal pain (5.1%), weight loss (4.8%), vomiting (4.2%), dizziness (3.9%), dyspnea (3.8%), pruritus (3.8%), insomnia (3.5%), dry mouth (3.5%), arthralgia (3.5%), back pain (3.2%), anorexia (3.2%), peripheral edema (2.9%), diarrhea (2.9%), increased cough (2.6%), tachycardia (2.6%), flatulence (2.6%), urinary tract infection (2.6%), somnolence (1.9%), vertigo (1.9%), oral paresthesia, and, pneumonia. Cases of interstitial lung disease have been reported in patients treated with riluzole, some of them severe; upon further investigation, many of these cases were hypersensitivity pneumonitis. If respiratory symptoms develop such as dry cough and/or dyspnea, chest radiography should be performed, and in case of findings suggestive of interstitial lung disease or hypersensitivity pneumonitis (e.g., bilateral diffuse lung opacities), riluzole should be discontinued immediately. In the majority of the reported cases, symptoms resolved after drug discontinuation and symptomatic treatment.

Dizziness, diarrhea, anorexia, and circumoral paresthesia occurred more frequently with 200 mg/day riluzole. In a study with approximately 4,000 patients given riluzole for ALS, three cases of neutropenia were reported within the first two months of treatment. Any

new medication has the potential for a rare, infrequent reaction of hypersensitivity, including anaphylaxis.

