#### 3. Attribution of Adverse Events:

Adverse events will be monitored for each subject participating in the study and attributed to the study procedures / design according to the following categories:

- a. Definite: Adverse event is clearly related to investigational procedures(s)/agent(s).
- b. Probable: Adverse event is likely related to investigational procedures(s)/agent(s).
- c. Possible: Adverse event may be related to investigational procedures(s)/agent(s).
- d. Unlikely: Adverse event is likely not to be related to the investigational procedures(s)/agent(s).
- e. Unrelated: Adverse event is clearly not related to investigational procedures(s)/agent(s).

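### A neutrophil count of 1500 or below is a reason to discontinue, but no entry criterion uses the screening blood count, so a patient who already meets that reason can be enrolled and dosed

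*Combined protocol and SAP*

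**What the plan says.** Section 11.B (Discontinuation of subjects) includes among its specific reasons "Evidence of neutropenia (ANC ≤ 1500) or other intolerable adverse reaction, or unable to tolerate study drug". It does not require a fall from the patient's own earlier count.

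The CBC is part of screening. Section 11.C.2 states "Routine laboratory studies include CBC, CMP, baseline HCG, TSH, fT4, RPR, ESR, CRP, urinalysis, and urine toxicology screen", and Table 1 marks the CBC at screening and at visits 4, 8 and 12 (days 28, 56 and 84).

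The inclusion and exclusion lists in section 7 name neither the CBC nor the ANC. The only laboratory value with a numeric entry limit is liver transaminase: "any liver transaminase level > 1.5 x ULN at initial screening, or > 5 x ULN during treatment". The nearest general exclusion is "Unstable medical illness as determined by the investigator". Section 9 adds that after a face-to-face evaluation "an experienced study investigator will determine suitability for enrollment".

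Section 12 names neutropenia as a riluzole risk. In about 4,000 treated ALS patients, "three cases of neutropenia were reported within the first two months of treatment".

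**The concern.** A stopping reason stated as an absolute level, on a test already done before dosing, would normally have a counterpart at entry or be defined relative to baseline. Here it has neither. A stable, asymptomatic patient with a screening ANC of, say, 1400 fails no listed criterion, yet already satisfies a listed reason for discontinuation before the first dose.

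Two things are at stake. The first is safety: such a patient could start a drug for which the protocol names neutropenia as a risk, and no entry rule would direct anyone to the count. The second is the tolerability data. Section 11 says the study is to give preliminary information on efficacy and tolerability. The stopping reason is worded alongside adverse reactions, and there is no control arm, so a count that was low all along could be taken for an effect of riluzole.

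**Working it through.** **1. Stopping reasons against entry limits.** The clinical and laboratory scores or values with a numeric stop in section 11.B compare as follows.

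| Measure | Stop (11.B) | Entry limit (section 7) | Relative to baseline? |
|---|---|---|---|
| Transaminases | > 5 x ULN | > 1.5 x ULN excluded | No, but has an entry limit |
| MADRS item 10 | 5 or more | excluded "by scoring 5 or more on the item-10 of the MADRS" | No, but has an entry limit |
| CAPS | 35% increase | not needed | Yes |
| CGI-I | 6 or more | not needed | Yes, the scale rates change |
| ANC | 1500 or below | none | No |

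(Section 12 words the MADRS screening limit slightly differently, as above 5. An entry limit exists either way.) ANC is the only row with neither an entry limit nor a baseline reference. No rationale is given, so this looks like an omission.

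**2. Timing, from Table 1.**
- First scheduled on-treatment CBC: visit 4, day 28.
- First scheduled on-treatment CAPS: visit 6, day 42.
- Gap: 42 − 28 = 14 days.

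A patient stopped on the day 28 result would have no scheduled CAPS while on drug. Section 11.C asks those who stop medication to keep attending, so CAPS at visits 6 and 12 may still be collected, off drug.

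**3. Possible scale.** The plan gives no figure to reproduce. The proportion of candidates with ANC of 1500 or below before treatment is not in the documents, so the prevalence q is an assumption, taken from 0.1% to 5%. Section 7 expects about 50 enrolled, but that number allows for screening failures as well as dropouts, and 20 are to complete. The number dosed, n, is therefore somewhere from 20 to 50.

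The chance of at least one such entrant, if none is excluded at discretion, is 1 − (1 − q)^n.

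| Assumed q | Expected in 50 (50q) | n = 50 | n = 20 |
|---|---|---|---|
| 0.1% | 0.05 | 4.9% | 2.0% |
| 0.5% | 0.25 | 22% | 9.5% |
| 1% | 0.5 | 39.5% | 18% |
| 2% | 1.0 | 64% | 33% |
| 5% | 2.5 | 92% | 64% |

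For example, at q = 1% and n = 50: 1 − 0.99^50 = 0.395. The width of the range shows that the documents cannot settle how likely the event is.

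**The case against.** The strongest reply is that the plan already has safeguards. The investigator decides on suitability with the screening results available, and can use the general medical exclusion. Both points stand: enrolment of such a patient is possible, not certain. But nothing directs the investigator to the ANC, and the general exclusion does not plainly cover a stable, symptom-free low count. For liver tests and suicidality the plan did not rely on discretion alone.

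Three stronger readings are tempting, and the documents do not support them.

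- A reader might infer that the patient must be stopped at day 28. Section 11.B says only that subjects may be discontinued. Mandatory wording appears elsewhere for transaminases, MADRS item 10 and CGI-I, but not for ANC. Because the ANC reason is worded together with adverse reactions, it can also be read as meaning neutropenia that arises on treatment. That ambiguity is part of what needs settling.
- A reader might infer that the case would be counted as a riluzole reaction. Section 13, item 3 requires each adverse event to be attributed on a five-level scale that includes unlikely and unrelated, and item 7 has the principal investigator review all adverse events as each subject completes. The screening CBC would be on file. Misattribution is a risk, because no rule compares the two counts, but the plan does not prescribe it.
- A reader might set one case in 50 (2%) against 3 in about 4,000 (3/4,000 = 0.075%) and call it a large excess. Any single event in 50 would give that contrast, whatever its cause, and section 12 does not define neutropenia for those patients. The comparison carries no weight.

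**Conclusion.** The gap is real and can be checked from the text alone: an absolute ANC stopping reason, a CBC drawn before dosing, and no entry criterion that uses it. As written, a patient who already meets the stopping reason can be enrolled and dosed unless excluded by judgement. A stop at day 28 would then leave no scheduled on-drug CAPS, and the low count could be misread as drug-related.

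This is a cheap improvement for patient safety and the tolerability data. Its effect on the primary analysis is small: at most an occasional early stop, in an intent-to-treat mixed model that uses all available data and may include later off-drug CAPS scores. The probabilities above rest wholly on an assumed prevalence, on independence between patients, and on no discretionary exclusion. They illustrate scale and are not estimates.

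**What to change.** Reconcile the exclusion criteria in section 7 with the discontinuation list in section 11.B, in one of two ways:

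- add an entry criterion that uses the screening CBC; or
- state how the ANC discontinuation reason applies relative to the patient's screening count.

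Any threshold, and the choice between the two, belongs to the sponsor and investigator. In the safety summaries, show each on-treatment low count beside the screening value, so that counts already low before dosing are distinguished from falls on treatment.

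The cost is about one line of protocol text and one extra column in a listing. No new test is needed, since the CBC is already drawn. The downside, if an entry criterion is chosen, is an occasional extra screen failure.

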## Audio Recording:

Clinician administered interviews may be audio recorded for inter-rater reliability and staff training purposes. Subject identifying information such as name, DOB, SSN, age, etc will not be on the audio recording. Recordings will be stored in a locked cabinet when not in use. Subjects will be asked on the consent form to indicate whether or not they agree to having their clinical interviews audio recorded. If subjects disagree to having their clinical interview audio recorded, it will not affect their eligibility to participate in study procedures.

#### **Data Analysis**

Descriptive statistics will be calculated prior to statistical analysis. Distributions of quantitative variables will be assessed for normality using normal probability plots and Kolmogorov-Smirnov statistics and transformations or non-parametric methods will be used as necessary. All statistical tests will be two-sided. Uncorrected alpha level of 0.05 will be used for testing the primary hypothesis. Pairwise post-hoc comparisons and tests of secondary outcome measures will be adjusted using Holm-Bonferroni procedure. All analyses will be intent-to-treat. We will using mixed effects regression models, with time effects for the primary outcome variable (CAPS). We do not expect significant moderating effects of alcohol use comorbidity but will assess the interaction between treatment and alcohol use comorbidity and perform follow-up tests as necessary. This approach will be applied to most secondary outcome measures as well. Mixed effects regression models use all available data on each subject, are flexible in modeling the correlation structure of the data and give unbiased results under missing at random

assumptions. In addition to testing the potential moderating effect of comorbid alcohol use described above, we will also perform exploratory analyses to the assess moderating effects of depression, medication status, substance abuse, age, and gender by adding these factors one at a time to the models above and testing interactions between each potential moderator and treatment group. Effects of intermittent missing data due to noncompliance with treatment schedule can also be assessed.

Table 1. Schedule of Study Events\*\*

	1 doie 1. Senedule of Study Events											
Visit	Screeni ng a	Baselin e	1	2&3	4	5,6,&7	8	9,10,11	12	month follow- up		
Day	0	0	7	14&21	28	35,42, & 49	56	63, 70, &77	84	114		
Informed Consent b	X											
Demographics	X											
SCID / MINI	X											
C-SSRS baseline	X											
MGH ATRQ	X											
ETI-SR, KLS, GPELS, CES	X											
M-MACE	X											
Psychiatric Evaluation	X											
BP, Pulse, Resp., Wt., Temp.	X	X	X	X	X	X	X	X	X			
ECG	X											
Physical Exam	X											
СВС	X				X		X		X			
СМР	X				LFTs		LF Ts		LFTs			
Serum Pregnancy (1)/ Urine Pregnancy (2)	X(1)	X (2)			X(2)		X( 2)		X(2)			
Urinalysis	X											
Inclusion/Exclusion	X											
CAPS	X	X °				X (visit 6 only)			X	X		
MADRS	X	X	X	X	X	X	X	X	X	X		
PCL, QIDS-SR, PSWQ, PSQI, SDS, SAFTEE		X	X	X	X	X	X	X	X	X		
Alcohol Consumption	X	X	X	X	X	X	X	X	X	X		
Drug Accountability		X	X	X	X	X	X	X	X	X		
Concomitant Meds	X	X	X	X	X	X	X	X	X			
Collect AEs and SAEs		X	X	X	X	X	X	X	X	X		
CGI-S/I and PGI-S/I		X	X	X	X	X	X	X	X	X		
Urine Toxicology	X	X							X			
Ethanol Breath Test/DAI		X							X			

				X (Visit			
Cogstate	Practice	X		6 only)		X	X
St. Luis University Mental							
Status Exam	X						

\*\* Day number reflects the approximate date, a window is allowed for scheduling and completion of the weekly study visits. a. Screening refers to the period between signing consent and completion of screening. As such this visit refers to one or multiple visits. b. Informed consent will be obtained prior to any study procedure. c. CAPS will be repeated at the discretion of the investigator or if 4 or more weeks elapsed since the prior CAPS. Abbreviations: Structured Clinical Interview for DSM (SCID), Mini International Neuropsychiatric Interview (MINI), Columbia-Suicide Severity Rating Scale (C-SSRS), MGH Antidepressant Treatment Response Questionnaire (MGH-ATRP), Early Trauma Inventory – Self Report (ETI-SR), Klein Loss Scale (KLS), Global Perceived Early-Life Stress (GPELS), Combat Exposure Scale (CES), Modified Military Acute Concussion Evaluation (M-MACE), Clinician Administered PTSD Scale (CAPS), Post Traumatic Stress Disorder Checklist (PCL), Montgomery-Asberg Depression Rating Scale (MADRS), Quick Inventory of Depressive Symptomatology – Self Report (QIDS-SR), Penn State Worry Questionnaire (PSWQ), Clinical Global Impression Severity/Improvement (CGI-S/I), Patient Global Impression-Severity/Improvement (PGI-S/I), Systematic Assessment for Treatment Emergent Events (SAFTEE), Pittsburgh Sleep Quality Index (PSQI), Electrocardiogram (ECG), Complete Blood Count (CBC), Comprehensive Metabolic Panel (CMP), Drug Attitude Inventory (DAI).

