# **Other Investigators and Study Personnel:**

[name]. †, M.D., [name]., M.P.H., [name], M.A.\* [name], A.P.R.N. †, [name], R.N.\*, [name] RN, BSN, MBA\*, [name], M.S., RN\*, [name].,\* [name], Psy.D., [name], B.S.\* [name]. †, [name]. †, [name], B.A.\*, [name], B.A.\*, [name], B.A.\*, [name], M.A.\*, [name], B.A.\*, [name].\*, [name].\*, [name].\*, [name], M.A.\*, [name]\*, [name], M.S.\*, [name], M.S.\*, [name], MMS\*

- \* Individuals who will be obtaining consent
- † Individuals authorized to prescribe study medication
- \* Individuals who will be obtaining consent
- † Individuals authorized to prescribe study medication
- **2. Title of Project:** An Investigation of the Effects of Riluzole in Patients with Post-Traumatic Stress Disorder (PTSD).
- **3. Purpose:** To conduct a pilot study evaluating the efficacy of riluzole 50 mg twice per day in decreasing symptoms of PTSD in patients diagnosed with PTSD.

Post Traumatic Stress Disorder (PTSD) is a debilitating and chronic mental illness with limited treatment options. Currently, there are only two FDA-approved medications both of which are monoaminergic antidepressants. Rates of non-response to these medications are high. The current study aims to examine the efficacy of a novel drug, riluzole, in treating PTSD symptoms. Riluzole is an FDA approved medication for Amyotrophic Lateral Sclerosis. Preclinical studies have shown riluzole to modulate glutamate release and clearance, and to have potent neuroprotective properties, promoting neuro-resilience. Other preclinical data also show the drug to have anxiolytic-like and antidepressant-like effects in rodent models of stress used to screen for antidepressant and anxiolytic activity. In addition, several open-label clinical studies further suggest riluzole has anxiolytic and antidepressant properties, even in patients who do not respond to standard monoaminergic antidepressant and anxiolytic medications. However, to date, riluzole has not been studied in patients suffering from PTSD. The proposed study will provide pilot data on the efficacy of riluzole in PTSD.

**4. Hypothesis:** We predict that riluzole will significantly reduce the symptoms of PTSD (measured by the Clinician Administered PTSD Scale-CAPS scores).

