SPECIFIC AIM 1: To provide preliminary data about the efficacy of riluzole treatment in improving PTSD symptoms. *Hypothesis*: PTSD subjects treated with

riluzole (50 mg twice per day for 12 weeks) will have reduction in PTSD symptoms. To examine the efficacy of riluzole we will compare the mean change in the CAPS total score over the course of 12 weeks of riluzole treatment.

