**6. Significance of proposed research:** Our proposed study is the first to examine the effect and feasibility of riluzole treatment for PTSD. Data from this pilot study will inform the design of future larger double-blind controlled studies. For e.g., if PTSD veterans showed full early response to riluzole following 1-4 weeks, this will affect the design of future definitive (likely multisite) studies. While placebo-controlled studies are standard for FDA approval and definitive clinical trials confirming efficacy, an open label approach is appropriate for pilot studies seeking early signals of efficacy and optimal treatment regimen. Pilot open label studies are essential for early phase of drug development.

**7. Experimental subjects**: We anticipate approximately 20 male and female subjects with PTSD, between the ages of 18-75 years, to complete all study procedures. In order to account for screenings failure and subject drop outs, and retain a sample of 20 subjects completing the treatment phase, approximately 50 eligible subjects will be enrolled.

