- 19. Systematic Assessment for Treatment Emergent Events (SAFTEE): The SAFTEE is a commonly used instrument originally developed by NIMH and adapted into a self-report instrument. It examines, in systematic fashion, possible treatment-emergent side effects and probes for specific adverse symptoms, including suicidal thoughts and behaviors, and self-injurious behavior.
- 20. Drug Attitude Inventory- (DAI): The DAI evaluates how attitudes about medications may affect treatment adherence. The items with the most potential for discrimination between dosing compliance and noncompliance are related to subjective 'feeling' factors.
- 21. Perceived Stress Scale (PSS): This is a 10-item self-report questionnaire to assess the severity of perceived stress over the past month.
- 22. Cumulative Adversity Interview (CAI): A multifaceted semi-structured assessment of stressful life events and chronic subjective stress used in research on stress and psychopathology.

Due to the potential of Riluzole to cause elevations in serum aminotransferase levels, liver function tests will be reviewed and monitored for medical significance (marking NCS for results not clinically significant) by the PI, a co-investigator or other medical research personnel (A.P.R.N., R.N. etc.). If any liver transaminase level is > 5X the UNL, the study investigator will be informed and the patient will be discontinued from the study, with appropriate medical follow-up.

PTSD subjects receiving the study medication will be seen weekly. Compliance with study medication will also be assessed weekly and at each visit. Subjects will be given medication diary cards to record the medication that they have taken at each daily dosing interval and the medication that was missed at each dosing interval. Drug accountability will then be done between the medication that was returned and the medication recorded as being taken on the diary cards. A subset of the interviews and measures obtained throughout the study will be repeated at a one-month, in person follow-up. This follow-up will be used to evaluate any lasting effects of the treatment, if any.

The presence of any spontaneously reported side effect or adverse event is carefully documented. Reasons for premature discontinuation of study medication, including intolerable side effects, are recorded; however, all willing subjects continue to return for weekly evaluations as if they remain on study medication.

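### Does leaving the primary time contrast unnamed put the week-12 CAPS change under two competing significance rules?

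*Combined protocol and SAP*

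**What the plan says.** The hypothesis in section 4 is directional in wording but names no visit: "We predict that riluzole will significantly reduce the symptoms of PTSD". Specific Aim 1, the only aim, states how efficacy will be examined: "we will compare the mean change in the CAPS total score over the course of 12 weeks of riluzole treatment".

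The Data Analysis section has three relevant statements:

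- On the primary test: "Uncorrected alpha level of 0.05 will be used for testing the primary hypothesis". All tests are two-sided.
- On everything after it: "Pairwise post-hoc comparisons and tests of secondary outcome measures will be adjusted using Holm-Bonferroni procedure".
- On the model: "We will using mixed effects regression models, with time effects for the primary outcome variable (CAPS").

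Table 1 schedules CAPS at screening (with a conditional repeat in the Baseline column), visit 6 (day 42), visit 12 (day 84) and the one-month follow-up (day 114). Of that last visit, section 11, C.3, says: "This follow-up will be used to evaluate any lasting effects of the treatment, if any".

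Section 7 aims for 20 completers and says "approximately 50 eligible subjects will be enrolled" to allow for screening failures and dropouts. There is one treatment and no control arm.

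**The concern.** With a single arm, the pairwise comparisons on CAPS in the main model can only be pairs of visits, and baseline versus week 12 is one of them. Two workflows therefore fit the words about time effects:

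1. The baseline-to-week-12 change is the primary test at 0.05.
2. The overall time effect is the primary test at 0.05, and the week-12 change is a Holm-adjusted follow-up.

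No sentence chooses, and the Holm family is not listed. The later moderator sentence does not help, since it speaks of "testing interactions between each potential moderator and treatment group" in a study with one group.

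If the week-12 contrast had the smallest p-value of the three visit pairs, a value between 0.05/3 = 0.0167 and 0.05 would count as significant under the first workflow and not under the second. An overall time effect also has no direction and could be driven by week 6 alone. An analyst who waited for the data before choosing would exceed 5% error. Two smaller questions go with it: which pre-dose CAPS is baseline, and whether the day-114 CAPS enters the model.

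**Working it through.** **Inputs.** From the documents: two-sided alpha 0.05, 20 completers, and three CAPS time points up to week 12. The documents give no effect size, SD or power, so the sample size cannot be reproduced; every effect below is an assumption.

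**Step 1. How much the label matters for the week-12 change.** On the paired-t scale the observed mean change needed is t(1 − α/2; n − 1)/√n, in SDs of the change. For n = 20, √n = 4.472:

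| Rule | α | t (19 df) | Change needed |
|---|---|---|---|
| Unadjusted | 0.05 | 2.09 | 0.47 SD |
| First Holm step, 3 pairs | 0.0167 | 2.63 | 0.59 SD |
| First Holm step, 6 pairs | 0.0083 | 2.94 | 0.66 SD |

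The six-pair row applies only if day 114 joins the same family. Section 11 presents that visit as a separate question about lasting effects, so three pairs is the relevant comparison.

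An assumed true change of 0.66 SD is the value that gives 80% power at n = 20 unadjusted. At that value, exact noncentral-t power is 80% at 0.05 and 63% at 0.05/3. The label would matter for the week-12 contrast if it were truly in doubt.

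**Step 2. Which rule each workflow gives the primary test.**

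| | Primary test | Its alpha | Week-12 change |
|---|---|---|---|
| Workflow 1 | Week-12 change | 0.05, unadjusted | Is the primary test |
| Workflow 2 | Overall time effect | 0.05, unadjusted | Secondary, Holm-adjusted |

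The primary test has one alpha in both rows, and Holm never touches it. The rules do not compete: one covers the primary hypothesis, the other covers what comes after.

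**Step 3. Error rate under no change.** I simulated 100,000 trials with n = 20, three visits, complete data and within-subject correlation 0.5. I used a paired t-test for week 12 and Hotelling's T² for the overall effect:

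- Week-12 test alone: 5.0%.
- Overall test alone: 5.0%.
- Either one significant: 7.7%.

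Other runs of the last figure gave 7.4 to 7.9%. Each workflow followed as written holds 5%. The excess requires choosing between them after seeing results.

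**Step 4. Which contrast is better.** Assumed changes in SD units, n = 20, three visits:

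| Pattern (week 6, week 12) | Week-12 test, 0.05 | Overall test, 0.05 |
|---|---|---|
| Steady: 0.33, 0.66 | 80% | 68% |
| Early and held: 0.66, 0.66 | 80% | 81% |
| Peak at week 6, half lost: 0.66, 0.33 | 29–30% | 68–73% |

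Neither contrast is better throughout.

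**Step 5. The smaller questions.** Table 1 places the conditional repeat CAPS in the Baseline column, so a repeat is naturally the baseline and otherwise the screening value serves.

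Adding day 114 to a model with categorical time leaves the week-12 estimate unchanged when data are complete, but not when some people miss week 12 and attend day 114. As a check, I took 30 subjects, with 10 missing week 12, 5 of whom returned at day 114, and correlation 0.5. The estimate shifted with an SD of about 0.02 visit SDs: real but negligible.

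**The case for a change.** The best case for acting is that Aim 1's wording does not fully settle the matter. A change described as taking place over 12 weeks also fits an overall time effect or a slope, and the hypothesis names no visit. An overall test followed by adjusted visit pairs is a routine mixed-model workflow, and the plan's mention of post-hoc pairwise comparisons hints at it. The label moves the threshold for the week-12 change from 0.47 to 0.59 SD. In the simulations at 0.66 SD, the week-12 change was significant unadjusted but not after Holm over three pairs in 11 to 17% of trials. One sentence would remove the doubt at no cost in patients or data.

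What stands: the primary contrast is not named, and a sentence naming it would be a harmless courtesy.

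What does not stand is that the plan contains a conflict. Calling the week-12 change post-hoc means treating the plan's only prespecified efficacy comparison as an afterthought. The larger figures sometimes attached to the point, such as six-pair families or a linear slope through day 114, rest on folding the follow-up visit into the primary question or on a linear time term that no sentence proposes. Results for 50 analysed subjects are also unrealistic, since section 7 sets that number to absorb screening failures and dropouts.

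**Conclusion.** No change is needed. The plan gives the primary hypothesis a single, correct rule, two-sided 0.05 without adjustment, and leaves a detail of model specification to the analyst. Aim 1 makes the baseline-to-week-12 CAPS change the natural choice. An overall time test would be an equally valid 5% test, and choosing between them is a trade-off that depends on an unknown time course.

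The inflation to about 7.5 to 8% assumes an analyst who picks the test from the results, which the plan does not invite. The Holm threshold of 0.59 SD would apply to the week-12 change only if the team had made the overall effect primary.

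The stakes are small in any case. Section 6 presents this as an open-label pilot looking for early signals to inform larger controlled studies, and no decision rule in the plan turns on p < 0.05. The thresholds need only n = 20 and a paired-t scale. The power and error figures also assume normal, equally correlated, complete data, and the power figures assume effect sizes that the documents do not give.
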